9.7.4 Immunogenicity

Immunogenicity assays will be performed on plasma. The assays will include detection of anti-capsid, and anti-FVIII total antibody, and determination of neutralizing antibodies against FVIII. Any increase in total antibody level, especially during the time period of 5-12 weeks, will be compared with FVIII activity measurements. Any abnormality of the liver parameters will lead to a retrospective immunogenicity assessment to determine anti-FVIII and capsid specific CTL. Anti-FVIII and capsid specific CTL assays will be performed on collected PBMCs.

Timing of assessment by these assays is provided in Table 9.1.2, Table 9.1.3, and Table 9.1.4.

9.7.5 Pharmacodynamics

The hFVIII antigen and activity level will be measured by an ELISA (antigen) and by one-stage APTT and/or chromogenic FXa assay (activity). Individual antigen and activity plasma plots will be prepared to assess changes over 16 weeks. FVIII activity measurements will be used to determine PD parameters.

If supported by FVIII activity data, non-compartmental analysis and observation will be used to estimate individual values of C_b (baseline concentration), C_{ss} (steady state concentration), T_{ss} (time to steady state), C(t) and AUC(0-t) where t is 16 weeks. Other parameters that may be used to describe individual FVIII protein and activity plasma profiles are C_{max} (maximum

BOMARIN	270-201 – Amendment 5	Page 55
---------	-----------------------	---------

concentration) and C_{avg} (average concentration, AUC(0-t)/t). The PD parameters and dose will be used to assess clinical pharmacology.

Sample collection times are indicated in Table 9.1.2, Table 9.1.3, and Table 9.1.4.

9.7.6 Exploratory Assessments

Blood samples will be collected from subjects at the time points indicated in Table 9.1.1, Table 9.1.2, Table 9.1.3, and Table 9.1.4 to evaluate biochemical, molecular, cellular, and genetic/genomic aspects relevant to Haemophilia A disease. The exploratory genetic/genomic testing is optional.

All biomarker samples collected in this study may be used for exploratory biomarker research including evaluation of additional biomarkers not specifically listed in the protocol. In addition, samples collected for other purposes may be used for exploratory use once the primary use has been completed.

On an exploratory basis, samples may be fractionated prior to shedding analysis in order to better characterize the presence and location of vector DNA and/or vector capsid within each matrix. The fractionation may be performed with samples collected specifically for shedding analysis (saliva, blood, semen, urine, faeces), or by using exploratory samples, such as plasma, PBMCs, and red blood cells, collected under the study protocol.

9.7.7 Haemo-QoL-A Quality of Life Assessment

The Haemo-QoL-A is a patient-reported outcome (PRO) questionnaire which will be used to assess subject quality of life (QoL) during the study. Assessments will occur at the time points listed in the Schedules of Assessments.

Details regarding the QoL assessment will be included in the Study Reference Manual.

9.7.8 Safety Variables

Safety in this study will be determined from evaluation of AEs, clinical laboratory assessments with a particular attention to the liver function, vital signs assessments, physical examinations, and immunogenicity.

9.7.8.1 Adverse Events

The occurrence of AEs will be assessed continuously from the time the subject signs the ICF. The determination, evaluation and reporting of AEs will be performed as outlined in Section 10. Assessments of AEs will occur at the time points shown in Table 9.1.1, Table 9.1.2, Table 9.1.3, and Table 9.1.4.

BOMARIN	270-201 – Amendment 5	Page 56
---------	-----------------------	---------

9.7.8.2 Clinical Laboratory Assessments

Specific visits for obtaining clinical laboratory assessment samples are provided in Table 9.1.1, Table 9.1.2, Table 9.1.3, and Table 9.1.4. The scheduled clinical laboratory tests are listed in Table 9.7.8.2.1. Refer to the Study Reference Manual for instructions on obtaining and shipping samples.

Any abnormal test results determined to be clinically significant by the Investigator should be repeated (at the Investigator's discretion) until the cause of the abnormality is determined, the value returns to baseline or to within normal limits, or the Investigator determines that the abnormal value is no longer clinically significant.

All abnormal clinical laboratory results should be initialed and dated by an Investigator, along with a comment regarding whether or not the result is clinically significant. Each clinically significant laboratory result should be recorded as an adverse event.

The diagnosis, if known, associated with abnormalities in clinical laboratory tests that are considered clinically significant by the Investigator will be recorded on the AE CRF.

Blood Chemistry	Haematology	Urine Tests	Other
Albumin	Haemoglobin	Appearance	CRP
BUN	Haematocrit	Color	
Calcium	WBC count	pН	Coagulation Screen
			including:
Chloride	RBC count	Specific gravity	APTT
Total cholesterol	Platelet count	Ketones	PT/INR
CO ₂	Differential cell count	Protein	TT
СРК		Glucose	
Creatinine		Bilirubin	
Glucose		Nitrite	
Phosphorus		Urobilinogen	
Potassium		Haemoglobin	
Total protein			
Sodium			
Uric Acid			

 Table 9.7.8.2.1:
 Clinical Laboratory Tests

BUN, blood urea nitrogen; CO₂, carbon dioxide; CRP, C-reactive protein; PT, prothrombin time; APTT, activated partial thromboplastin time; RBC, red blood cell; WBC, white blood cell; TT, thrombin time; INR, international normalized ratio.

BOMARIN	270-201 – Amendment 5	Page 57
---------	-----------------------	---------

9.7.8.3 Liver Function and Hepatitis Testing

Subjects will be screened for evidence of previous hepatitis B or hepatitis C infection at Screening. Subjects with documented results showing an absence of active Hepatitis B or Hepatitis C infection (as measured by positive surface antigen for hepatitis B or positive RNA testing for hepatitis C) 30 days prior to providing signed informed consent do not need to be screened again.

Evidence of ongoing Hepatitis B or Hepatitis C infection is exclusionary. Subjects who have cleared a Hepatitis B infection or are seronegative do not need to receive the Hepatitis B vaccination.

Subjects will be tested for hepatitis B and hepatitis C reactivation at Week 16. Subjects who receive therapeutic corticosteroids prior to Week 16 do not need to complete the Week 16 reactivation assessment; instead, they will be tested for hepatitis B and hepatitis C reactivation at the time points listed in Table 9.1.5.

A liver ultrasound and liver function testing at Screening will identify any significant hepatic dysfunction, which is defined as:

- More than 3x the normal ALT level
- More than 3x the normal bilirubin level
- More than 3x the normal Alkaline phosphatase level.
- INR \geq 1.4.
- Thrombocytopoenia under $100 \ge 10^9/L$
- Liver ultrasound results indicative of a liver cirrhosis

Liver function tests will be monitored on a regular basis, at the time points indicated in Table 9.1.1, Table 9.1.2, Table 9.1.3, and Table 9.1.4. At each time point, the following LFTs should be assessed:

 Table 9.7.8.3.1: Liver Function Tests

Liver Function Tests			
Alkaline Phosphatase	AST (SGOT)	Total Bilirubin	LDH
ALT (SGPT)	Direct Bilirubin	GGT	

ALT, alanine aminotransferase; AST, aspartate aminotransferase; GGT, gamma-glutamyltransferase; LDH, lactate dehydrogenase; SGOT, serum glutamic-oxaloacetic transaminase; SGPT, serum glutamic-pyruvic transaminase

BOMARIN	270-201 – Amendment 5	Page 58
---------	-----------------------	---------

Patients with ALT > 1.5 ULN during the study may undergo additional evaluations (e.g., imaging studies including MRI or ultrasound, additional blood tests, and/or liver biopsy) at the discretion of the investigator.

9.7.8.4 HIV Testing

HIV testing will be performed at Screening. Subjects with documented negative results within the last 30 days prior to screening do not need to be retested.

9.7.8.5 Vital Signs, Physical Examinations and Other Observations Related to Safety

Vital signs will include seated systolic and diastolic blood pressure, heart rate, respiration rate, and temperature. Any clinically significant change in vital signs will be recorded as an AE.

Systolic blood pressure, diastolic blood pressure, heart rate, respiration rate, and temperature will be assessed at Screening, Baseline, and at the beginning of each visit during the Post-Infusion Follow-Up and Safety Follow-Up periods. On the day of the BMN 270 Infusion, vital signs will be monitored prior to infusion, during the infusion every 15 minutes (\pm 5 minutes), following the infusion hourly (\pm 5 minutes) for 6 hours and then every 2 hours (\pm 15 minutes) for 6 hours and then at 4 hour intervals (\pm 15 minutes).

A complete physical examination is necessary during Screening/Baseline, at Week 16 and 52 and every 52 weeks thereafter; at other visits, brief physical examinations may be performed at the discretion of the investigator based on the subject's clinical condition. Particular attention should be given to signs of bleeding, as well as assessing possible hemarthroses.

A complete physical examination will include general appearance (head, eyes, ears, nose, and throat), cardiovascular, dermatologic, lymphatic, respiratory, gastrointestinal, genitourinary, musculoskeletal, and neurologic systems.

A brief physical examination will include general appearance, cardiovascular, respiratory, neurologic, and gastrointestinal assessments.

Height will be recorded at Screening only. Weight will be recorded at Screening and then every 6 months thereafter.

9.7.8.6 Vector Shedding

Vector shedding has been extensively studied in all similar clinical trials performed to date. (Nathwani, 2014, N.Engl.J.Med.); (Manno, 2006, Nat.Med.); (Schenk-Braat, 2007, J.Gene Med.); (Croteau, 2004, Ann.Occup.Hyg.). In the literature referenced above, including Haemophilia B clinical studies utilizing AAV2 and AAV8, vector was no longer detectable

BOMARIN	270-201 – Amendment 5	Page 59
---------	-----------------------	---------

after 40 days in blood, saliva, urine or stool, but in one study was detected in the seminal fluid but not in motile sperm (Manno, 2006, Nat.Med.). In these studies, the amount of vector present in these bodily fluids involved an extremely small fraction of the infused dose. More recent data from an ongoing AAV-FIX study demonstrates persistence of the vector in both the blood and the semen for at least 39 weeks (Miesbach, 2016, Haemophilia).

During the Post-Infusion Follow-Up period, subjects will undergo testing of various bodily samples to look for evidence of vector shedding for possible viral transmission. Bodily fluids will be tested by PCR at the time points indicated in Table 9.1.2, Table 9.1.3, and Table 9.1.4. Fluids tested will include:

- Blood
- Saliva
- Semen
- Urine
- Stool

Vector shedding will also be extensively studied in the present clinical trial, every other week between Weeks 4-16, then every 4 weeks to Week 52 until at least 3 consecutive negative results are obtained. Testing of semen will continue through Week 12, even if 3 consecutive negative results have been recorded in that compartment prior to that timepoint. Subjects who have not had 3 consecutive negative samples by Week 52 should continue to have PCR testing every 4 weeks until 3 consecutive negative samples are documented (or upon consultation between the Investigator and Medical Monitor).

Contraception use may need to be extended beyond 26 weeks in individual subjects based on observed vector shedding in semen. After 6 months, subjects may stop contraception use only if they have had 3 consecutive negative semen samples.

Details for sample collection and storage are provided in the Laboratory Manual.

BOMARIN	270-201 – Amendment 5	Page 60
---------	-----------------------	---------

10 REPORTING ADVERSE EVENTS

10.1 Safety Parameters and Definitions

Safety assessments will consist of monitoring and recording protocol-defined AEs and SAEs; measurement of protocol-specified haematology, clinical chemistry, and urinalysis variables; measurement of protocol-specified vital signs; and other protocol-defined events of special interest that are deemed critical to the safety evaluation of the study drug.

10.1.1 Adverse Events

For this protocol, a reportable adverse event (AE) is any untoward medical occurrence (e.g., sign, symptom, illness, disease or injury) in a subject administered the study-drug or other protocol-imposed intervention, regardless of attribution. This includes the following:

- AEs not previously observed in the subject that emerge during the course of the study.
- Pre-existing medical conditions judged by the Investigator to have worsened in severity or frequency or changed in character during the study.
- Complications that occur as a result of non-drug protocol-imposed interventions (eg, AEs related to screening procedures).

An adverse drug reaction is any AE for which there is a reasonable possibility that the study-drug caused the AE. "Reasonable possibility" means there is evidence to suggest a causal relationship between the study-drug and the AE.

Bleeding events that are normal events of haemophilia (ie, bleeding events which occur only because the subject is a haemophiliac) should not be recorded as AEs but will instead be captured in subject diaries. Bleeding events that occur where a normal (ie, non-haemophiliac) patient would bleed, such as bleeding as a result of major trauma, should be recorded as adverse events. All bleeding events which meet criteria for being serious should be reported as serious adverse events (SAEs) whether or not they are bleeding events that are normal sequelae of haemophilia.

Whenever possible, it is preferable to record a diagnosis as the AE term rather than a series of terms relating to a diagnosis.

BOMARIN	270-201 – Amendment 5	Page 61
---------	-----------------------	---------

10.2 Serious Adverse Events

A serious adverse event (SAE) is any untoward medical occurrence that at any dose meets 1 or more of the following criteria:

- Is fatal
- Is life threatening

Note: Life-threatening refers to an event that places the subject at immediate risk of death. This definition does not include a reaction that, had it occurred in a more severe form, might have caused death.

- Requires or prolongs inpatient hospitalization.
- Results in persistent or significant disability or incapacity
- Is a congenital anomaly or birth defect in the child or fetus of a subject exposed to IP prior to conception or during pregnancy
- Is an important medical event or reaction that, based on medical judgment, may jeopardize the subject or require intervention to prevent one of the above consequences (e.g. anaphylaxis)

All adverse events that do not meet any of the criteria for SAEs should be regarded as nonserious AEs.

10.2.1 Events of Special Interest (EOSI)

The following EOSI need to be reported to the Sponsor within 24 hours of site awareness, irrespective of seriousness, severity or causality:

• Elevation of liver enzymes (ALT) that triggers an initiation or modification of corticosteroid treatment

10.3 Methods and Timing for Capturing and Assessing Safety Parameters

10.3.1 Adverse Event Reporting Period

The study AE reporting period is as follows: After informed consent but prior to initiation of study treatment, only SAEs associated with any protocol-imposed interventions will be reported. After informed consent is obtained and the first administration of study drug, the reporting period for all non-serious AEs and SAEs begins and continues for approximately 5 years or until study discontinuation/termination, whichever is longer. The criteria for determining, and the reporting of SAEs is provided in Section 10.2.

BOMARIN	270-201 – Amendment 5	Page 62
---------	-----------------------	---------

10.3.2 Eliciting Adverse Events

Investigators will seek information on AEs, SAEs, and EOSI at each subject contact by specific questioning and, as appropriate, by examination. Information on all AEs and SAEs and EOSI, should be recorded in the subject's medical record and on the AE Case Report Form (eCRF).

10.3.3 Assessment of Seriousness, Severity, and Causality

The Investigator responsible for the care of the subject or medically qualified designee will assess AEs for severity, relationship to study drug, and seriousness (refer to Section 10.2 for SAE definitions). These assessments must be made by a study clinician with the training and authority to make a diagnosis (eg, MD/DO, physician's assistant, nurse practitioner, or DDS).

10.3.3.1 Seriousness

The investigator will assess if an AE should be classified as "serious" based on the seriousness criteria enumerated in Section 10.2. Seriousness serves as a guide for defining regulatory reporting obligations.

10.3.3.2 Severity

Severity (as in mild, moderate, or severe headache) is not equivalent to seriousness, which is based on subject/event outcome or action criteria usually associated with events that pose a threat to a subject's life or functioning. The severity of each will be assessed using the defined categories in Table 10.3.3.2.1.

The Investigator will determine the severity of each AE and SAE and EOSI using the NCI CTCAE v4. Adverse events that do not have a corresponding CTCAE term will be assessed according to the general guidelines for grading used in the CTCAE v4 as stated below.

BOMARIN	270-201 – Amendment 5	Page 63
---------	-----------------------	---------

Grade	Description		
1	Mild: asymptomatic or mild symptoms; clinical or diagnostic observati indicated	ons only; intervention not	
2	Moderate: minimal, local or noninvasive intervention indicated; limiting age-appropriate instrumental activities of daily living (ADL) ^a		
3	Severe or medically significant but not immediately life-threatening: hospitalization or prolongation of hospitalization indicated; disabling; limiting self-care ADL ^b		
4	Life threatening or debilitating: consequences; urgent intervention indicated	Grade 4 and 5 AEs should always be	
5	Death related to AE	reported as SAEs	

^a Instrumental ADL refer to the following examples: preparing meals, shopping for groceries or clothes, using the telephone, managing money.

^b Self-care ADL refer to the following examples: bathing, dressing and undressing, feeding oneself, using the toilet, taking medications, not bedridden.

10.3.3.3 Causality

The Investigator will determine the relationship of an AE to the study drug and will record it on the source documents and AE CRF. To ensure consistency of causality assessments, Investigators should apply the guidance in Table 10.3.3.3.1.

BIOMARIN	270-201 – Amendment 5	Page 64
----------	-----------------------	---------

Relationship	Description	
Not Related	• Exposure to the IP has not occurred	
	• OR	
	• The administration of the IP and the occurrence of the AE are not reasonably related in time	
	• OR	
	• The AE is considered likely to be related to an etiology other than the use of the IP; that is, there are no facts, evidence, or arguments to suggest a causal relationship to the IP.	
Related	The administration of the IP and the occurrence of the AE are reasonably related in time	
	AND	
	• The AE could possibly be explained by factors or causes other than exposure to the IP	
	OR	
	• The administration of IP and the occurrence of the AE are reasonably related in time	
	AND	
	• The AE is more likely explained by exposure to the IP than by other factors or causes.	

Factors suggestive of a causal relationship could include (but are not limited to):

- Plausible temporal relationship
- Absence of alternative explanations
- Rarity of event in a given patient or disease state
- Absence of event prior to study drug exposure
- Consistency with study product pharmacology
- Known relationship to underlying mechanism of study drug action
- Similarity to adverse reactions seen with related drug products
- Abatement of AE with discontinuation of study drug, and/or recurrence of AE with reintroduction of study drug

BOMARIN	270-201 – Amendment 5	Page 65
---------	-----------------------	---------

The investigator's assessment of causality for individual AE reports is part of the study documentation process. Regardless of the Investigator's assessment of causality for individual AE reports, the Sponsor will promptly evaluate all reported SAEs against cumulative product experience to identify and expeditiously communicate possible new safety findings to investigators and applicable regulatory authorities.

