14.6 Safety Analysis

The Medical Dictionary for Regulatory Activities terminology (MedDRA) will be used by the Sponsor to assign system organ class and preferred term classification to events and diseases, based on the original terms entered on the CRF.

All AEs will be coded using MedDRA. The incidence of AEs will be summarized by system organ class, preferred term, relationship to study drug, and severity. A by-subject listing will be provided for those subjects who experience a serious AE (SAE), including death, or experience an AE associated with early withdrawal from the study or study drug. Hepatitis is of interest, and the percentage of subjects who report hepatitis will be presented.

Clinical laboratory data will be summarized by the type of laboratory test. For each clinical laboratory test, descriptive statistics will be provided on Baseline as well as all subsequent visits. Descriptive statistics for physical examination results and vital signs will also be provided.

Detailed statistical methods will be provided in the SAP.

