9.3.3.1 Study Safety Evaluation Criteria

If any of the following events occur in a subject in the study who has received BMN 270 infusion, enrollment into the trial will be put on halt to complete an extensive safety analysis per Section 9.1.

Proprietary and Confidential

BOMARIN	270-201 – Amendment 5	Page 47
---------	-----------------------	---------

- Any ALT elevation > 5x ULN for at least 2 consecutive weeks after administration of BMN 270, in the absence of a definitive alternate etiology for the increase
- The occurrence of Grade 3 or higher adverse events (excluding ALT elevation) assessed as related to study drug, including liver failure and clinical hepatitis
- The detection of neutralizing antibodies to hFVIII following BMN 270 infusion
- The detection of AAV vector DNA in the semen of a participant in 3 consecutive samples (which are at least 2 weeks apart) more than 52 weeks after BMN 270 infusion, as discussed in Section 9.7.8.6
- The occurrence of a malignancy excluding skin cancers at any point after BMN 270 infusion

If the following event occurs in a subject in the study who has received BMN 270 infusion, a DRB review and analysis of safety data will be undertaken to determine whether the enrollment into the trial will be put on halt:

• Grade 2 adverse event assessed as related to study drug that persists for at least 7 days

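### The first limb of 'Related' in the causality table never asks whether BMN 270 could be the cause, and the table's two categories overlap and leave a gap

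*Protocol*

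**What the plan says.** Section 10.3.3.3 tells investigators to apply Table 10.3.3.3.1 so that causality is assessed consistently. The table has two categories.

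*Related* has two limbs joined by OR. Both need timing: "The administration of the IP and the occurrence of the AE are reasonably related in time". The first limb adds "The AE could possibly be explained by factors or causes other than exposure to the IP". The second adds "The AE is more likely explained by exposure to the IP than by other factors or causes".

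*Not Related* has three limbs joined by OR: no exposure; timing not reasonable; or "The AE is considered likely to be related to an etiology other than the use of the IP", which the table explains as there being nothing to suggest a causal link to the investigational product (IP).

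Below the table is a list of factors that point towards causality. One of them is "Absence of alternative explanations".

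Section 10.1.1 gives the protocol's own standard. An adverse drug reaction needs a reasonable possibility of causation, which "means there is evidence to suggest a causal relationship between the study-drug and the AE".

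The classification is used in three places. Section 9.3.3.1 halts enrolment on "The occurrence of Grade 3 or higher adverse events (excluding ALT elevation") when the event is assessed as related. The same section sends a related Grade 2 event lasting at least 7 days to the Data Review Board (DRB). Section 14.6 of Amendment 6 (14.5 in Amendment 5) states: "The incidence of AEs will be summarized by system organ class, preferred term, relationship to study drug, and severity".

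**The concern.** The first *Related* limb asks two things: was the timing reasonable, and could something else explain the event? The second answer argues against the IP, yet here it counts towards relatedness. The limb was probably meant to say that the IP is a possible cause even though others are possible too, but the half about the IP is missing.

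Safety is a primary objective, at most 15 subjects are dosed, and a single related Grade 3 or higher event (ALT elevation excepted) is enough to halt enrolment. If two investigators can file the same event in opposite categories and both be following the table, the halt, the DRB review and the relationship tables reflect reading habits as well as the drug. Relatedness has also already supported a design decision: Amendment 4 softened the automatic Grade 2 halt partly because none of the 9 subjects dosed by then had had a related Grade 2 event lasting 7 days or more.

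**Working it through.** The plan gives no figure to reproduce, because the question is about wording. The check treats the table as a rule and lists every pattern it can meet.

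**Conditions, from Table 10.3.3.3.1**

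- T: timing is reasonable. (No exposure is covered by T being false.)
- A: another cause could explain the AE.
- L: another cause is likely and nothing suggests the IP. This implies A and rules out M.
- M: the IP is more likely than other causes.

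**Rules as written**

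- Related = T and (A or M)
- Not Related = (not T) or L

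**Admissible patterns.** For each value of T, L true allows one pattern (A true, M false) and L false allows four. That gives 2 × (1 + 4) = 10 patterns. The five with T false are all Not Related only. The five with T true are:

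| A: other cause possible | L: other cause likely, nothing for IP | M: IP more likely | Meets Related | Meets Not Related | Outcome |
|---|---|---|---|---|---|
| yes | yes | no | yes | yes | both |
| yes | no | yes | yes | no | Related only |
| yes | no | no | yes | no | Related only |
| no | no | yes | yes | no | Related only |
| no | no | no | no | no | neither |

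**What follows**

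1. *Overlap.* In the first row the AE meets both categories, and the table does not say which prevails. An example can be built from Section 9.4.8.2.1, which allows an 11-week prednisolone taper. Suppose an AE in that window is judged reasonably timed after infusion but likely due to prednisolone, with nothing pointing to BMN 270. The first *Related* limb and the third *Not Related* limb both apply.
2. *Gap.* In the last row the AE meets neither category. This is the lesser defect, since an event with no other possible cause would often be judged more likely due to the IP. An event of undetermined cause can still land there.
3. *No discrimination on the IP.* Whenever T and A hold, the *Related* row is met whatever the value of M.
4. *Wrong direction.* Compare the third row with the fifth. Adding a possible alternative cause moves the event from neither category to Related. The factor list in the same section treats the lack of an alternative as the sign of causality.
5. *Against Section 10.1.1.* That section asks for evidence of a causal link. The first *Related* limb contains no evidence term beyond timing.

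**Version check.** The wording is identical in Amendments 4 and 5. Section 10.3.3.3 of Amendment 6 is not in the available text. The Amendment 6 revision table lists no change to Sections 9.3.3.1, 10.1.1 or 10.3.3.3, so carry-forward is likely but not confirmed.

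**The case against.** The strongest reply is that the table is guidance to a clinician and not an algorithm. The investigator determines relationship using the table together with a list of factors. Read as a whole, the first *Related* limb looks like a cautious 'possible' category on a two-level scale, and over-attribution errs on the safe side in a first-in-human study. The sponsor evaluates every serious AE whatever the investigator's assessment, a halt leads to a safety review and a possible restart, and AEs are also summarised by organ class, preferred term and severity. The Amendment 4 rationale, with no persistent related Grade 2 event among 9 subjects, also fits poorly with near-automatic attribution.

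Much of this stands, and it limits the point. A reader might infer that every timely AE with another possible cause will be recorded as related. The documents do not support that, because the third *Not Related* limb lets an investigator file an event with a likely other cause as not related. A reader might also want a probability of a spurious enrolment halt. None can be supported: the documents give no background rate of Grade 3 or higher events, and a halt matters only while enrolment is open, a period for which they give no person-time. Once the last subject is dosed, that consequence lapses.

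The reply does not remove the overlap or the missing reference to the IP. A table issued to make assessments consistent should not place one event in both categories, and the likely intention is not what is written.

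**Conclusion.** The point holds as a defect of definition. The first *Related* limb does not require the IP to be a possible cause. It contradicts Section 10.1.1 and the factor list, and it leaves the two categories neither mutually exclusive nor exhaustive: of five timely patterns, one meets both and one meets neither. How often those patterns occur is unknown. The error can run either way, inflating drug-related incidence where the limb is read literally and leaving the result to personal judgement where it is not.

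The consequence is that the enrolment halt, the Grade 2 DRB review and the relationship tables depend on an unstated choice of row. With at most 15 subjects, a few differently filed events would show in the tables. An analysis plan cannot repair this, because the classification is made by the investigator at source. The conclusion assumes that Amendment 6 carries the Amendment 5 wording forward. It should be corrected, but it does not undermine the design.

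**What to change.** Reconcile the table with Section 10.1.1:

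- Reword the first *Related* limb so that it needs reasonable timing AND evidence suggesting a reasonable possibility that the IP caused or contributed to the AE, even if other causes are also possible.
- Keep the limb for events more likely explained by the IP.
- Define *Not Related* as everything that does not meet *Related*, so that each AE falls in exactly one category.
- Leave the halt and review thresholds in Section 9.3.3.1 as they are.

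Apply the new wording prospectively. A retrospective re-review is optional. Because the study is open-label and outcomes are known, any re-review should keep the original assessments as the record and be reported as a sensitivity listing.

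The cost is an amendment to one table and a note to sites, plus a review of AEs in at most 15 subjects if the sensitivity listing is wanted. The downside is that a few AEs may change category and slightly fewer may count as related, which slightly narrows the input to the halt rule. The amendment should say so.
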